# Study Protocol

Official Title : Comparison of Operating Conditions, Postoperative Recovery and Overall Satisfaction Between Deep and Restricted Neuromuscular Blockade for Spinal Surgery Under General Anesthesia

Identifiers : NCT02724111

Date of Document : 4th February 2016

Protocol of the Research	
1.1 Objectives & Hypotheses	
* Objectives
 
Primary Outcome Measure(s):
 
 
1. Mean Value of Peak Inspiratory Pressure [Time Frame: Every 15 minutes during anesthesia]
 
 
Secondary Outcome Measure(s):
 
 
2. Mean Value of Pressure of Back Muscle Retractor [Time Frame: Every 15 minutes during the placement of the retractor]
 
3. Overall Satisfaction of Surgeons for the Surgical Condition [Time Frame: After surgery]
 
4. The Muscle Tone [Time Frame: at the screw insertion through the pedicle of spine during surgery]
 
5. The Number of Body Movements [Time Frame: Throughout the surgery]
 
6. The Degree of Bleeding [Time Frame: Throughout the surgery]
 
7. Recovery Time (Time to Reach Sedation Score 5 at Post-anesthesia Care Unit (PACU). [Time Frame: every 10 min for 1 hour at PACU.]
 
8. Adverse Events [Time Frame: during the postoperative 24 hours]
 
 
* Clinical hypotheses
 
 
(1) Mean value of peak inspiratory pressure (PIP) is lower in deep NMB group than in restricted NMB group. The higher PIP in restricted NMB group is related to the more surgical bleeding compared to deep NMB group.
 
(2) Operating conditions including the number of body movement, degree of bleeding and muscle tone in deep NMB group are superior to restricted NMB group.
 
(3) Overall satisfaction of surgeons in deep NMB group is superior to restricted NMB group.
 

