
1.3 Study Design
	
Group treatment (Arms): Group RB, group treated restricted NMB; Group DB, group treated with deep NMB → randomized allocation (subjects: MEP not monitored surgeries)
 
Inclusion criteria: Ninety ASA class I-II adults, aged 18-75 years, scheduled for elective spinal surgery (lumbar surgeries which have lesions no more than 3 spinal levels and not monitored by MEP) of duration >1 hour and prone position under TIVA
 
Exclusion criteria: Pregnancy, the receipt of medication known to interfere with neuromuscular blockade, diseases affecting neuromuscular transmission, and the history of hypersensitivity on rocuronium or sugammadex. The patients who will have hemodynamic instability, mean blood pressure increase or fall of > 30% from baseline (lasting for more than 5min), and blood loss > 1 L during surgery, and MEP monitored surgeries.
 
Monitoring devices: An electrocardiograph, pulse oximetry probe, esophageal temperature probe, entropy sensor (Datex Ohmeda) and noninvasive blood pressure cuff or invasive arterial and central vein lines will be applied to patients before or after anesthesia induction. The neuromuscular blockade will be monitored with a train-of-four (TOF, frequency 2 Hz, current 50 mA, interval 15 s) using an accelerator device (TOF-Watch SX; Organon Ltd, Ireland). The stimulation electrodes will be placed on the wrist at the level of the ulnar nerve, and the accelerometer will be placed at the distal part of the thumb. The skin temperature on the patient's thenar will be maintained above 32°C throughout the study by wrapping the arm in cotton. The TOF ratio (T4/T1) and T1 value will be displayed on the screen and recorded. State entropy will be used as a guide for anesthetic depth and it will be maintained at 40 to 60 during surgery.

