
1.5 Study Procedures
 
* Blinding and measure of outcomes
 
· A double blinded approach will be used in this trial: randomization for group allocation and allocation concealment will be kept in this study. In the operating room, induction and maintenance (including the operation of TOF-Watch) of anesthesia will be performed by independent anesthesiologists not involved in the study and they are not blinded to the group allocation of patients. However, all surgeons will be blinded and so the evaluation of muscle tone of each patient scaled by surgeons will be blinded. Also, after the end of surgery, a blinded, independent investigator will assess the patients during the emergence and recovery phases. Postoperative outcomes including recovery time and surgeon satisfaction will be measured by the investigator blinded to the group assignment.
 
➔ If the patients show any body movement during surgery or if surgeons express any complaint about muscle tone (the muscle tone: grade 3), rescue rocuronium 5 mg will be administered and the number of body movements and rescue rocuronium administration (dose) will be recorded.
 
➔ The extubation criteria are as follows: TOF ratio > 0.9, BIS > 70, regular respiratory pattern, tidal volume of at least 5 ml/kg and SpO2 > 95% when the patient breathes spontaneously.
 
* Drug treatment
 
· Premedication: midazolam 2 mg, i.m (in all patients)
 
· Induction: In all patients, after lidocaine 40 mg, i.v, effect-site concentration (CE) of propofol will be increased stepwise from the initial CE of 2.0 µg/mL until loss of the eyelash reflex (or arrival of state entropy less than 60), and then the TOF-Watch will be calibrated using the automatic calibrating procedure as soon as the patient is asleep. The first response in the TOF sequence (T1) will be defined as the baseline value to which all subsequent responses are compared. Effect-site concentration of remifentanil will be then fixed to 1.5 ng/mL and rocuronium 1 mg/kg will be injected and the patients will be tracheally intubated at arrival of minimum T1 height.
		

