	
· Ventilator settings: Tidal volume 8 mL/kg, respiratory rate initially 10 to 12 breaths/min, positive end-expiratory pressure (PEEP) 4 cmH2O and inspiratory-to-expiratory time ratio 1:2. Mechanical ventilation (respiratory rate) will be adjusted to maintain an end-tidal partial pressure of carbon dioxide at between 30 and 35 mmHg during surgery.
 
· Maintenance: The patients will be allocated to one of the 2 groups receiving either DEEP NMB (group DB) or RESTRICTED NMB (group RB) according to the assignment using a computer random number generator.
 
· NMB: In the group DB, rocuronium will be administered to maintain deep NMB (TOF count 0, PTC of 1-2 twitches) until the end of surgery and the reversal of NMB will be performed by sugammadex 4 mg/kg.
 
In the group RB, sugammadex will be administered according to the prescribing indications (4 mg/kg for deep NMB state or 2 mg/kg for moderate NMB or less) to reverse the NMB 10 min after position change (10 min after placing the patient prone). Thereafter, muscle relaxants will not be injected any more throughout the surgery except the following situations: If the patients show any body movement during surgery or if surgeons express any complaint about muscle tone (the muscle tone: grade 3), rescue rocuronium 5 mg will be administered and the number of body movements and rescue rocuronium administration (dose) will be recorded.

1.6 References	
 
Edmonds HL Jr, Paloheimo MP, Backman MH, Johnson JR, Holt RT, Shields CB. Transcranial magnetic motor evoked potentials (tcMMEP) for functional monitoring of motor pathways during scoliosis surgery. Spine (Phila Pa 1976) 1989;14(7):683-6.
 
 
Kalkman CJ, Drummond JC, Kennelly NA, Patel PM, Partridge BL. Intraoperative monitoring of tibialis anterior muscle motor evoked responses to transcranial electrical stimulation during partial neuromuscular blockade. Anesth

Analg 1992;75(4):584-9.

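### Blood loss above 1 L during surgery is an exclusion criterion, so patients are removed after allocation on an extreme of a bleeding outcome; if the trial's hypothesis holds, the bleeding comparison is pulled toward no difference.

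*Protocol*

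**What the plan says.** **The rule.** The exclusion criteria in Protocol section 1.3 begin with conditions that can be checked before surgery. They then add "The patients who will have hemodynamic instability, mean blood pressure increase or fall of" more than "30% from baseline (lasting for more than 5min), and blood loss" of more than "1 L during surgery, and MEP monitored surgeries".

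**Allocation and when the arms diverge.** Under Maintenance in section 1.5, "The patients will be allocated to one of the 2 groups receiving either DEEP NMB (group DB) or RESTRICTED NMB (group RB") by computer-generated random numbers. Both arms get the same induction. They separate when RB receives sugammadex "to reverse the NMB 10 min after position change (10 min after placing the patient prone").

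**Bleeding as an outcome.** Section 1.1 lists as secondary outcome 6 "The Degree of Bleeding [Time Frame: Throughout the surgery"]. Hypothesis (1) states: "The higher PIP in restricted NMB group is related to the more surgical bleeding compared to deep NMB group". Hypothesis (2) includes bleeding among the operating conditions expected to be better in DB. The SAP compares a 6-point surgeon rating of bleeding by Mann-Whitney U-test.

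**Analysis population.** The SAP text supplied for this review names no analysis population and has no rule for a patient who meets an exclusion criterion after allocation. It only allows for 15% drop-out.

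**The concern.** Randomisation protects a comparison only if who is analysed does not depend on what happened after allocation. Here removal depends on blood loss, which accrues essentially all under the assigned blockade and which the protocol itself expects to differ by arm. It is also close to an outcome: patients losing more than 1 L are likely to be those with the worst bleeding ratings.

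The direction follows from the sponsor's own hypothesis. If RB bleeds more, the upper tail is cut more heavily in RB, and the patients who remain look more alike than the randomised groups were. The rule thus works against finding the bleeding benefit the trial expects. Any effect on the primary outcome is indirect, through the link between airway pressure and bleeding that the protocol asserts.

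The blood pressure criterion is a lesser problem. It too can be met after allocation, but some cases may arise before the arms diverge. No arm effect on blood pressure is hypothesised, so the direction of any bias is unknown.

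**Working it through.** **The plan's own figure.** The only stated calculation is for peak inspiratory pressure (PIP), from pilot values of 18.8 (SD 2.9) and 20.7 (SD 3.0) cmH2O.

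- Pooled SD = √((2.9² + 3.0²)/2) = 2.950, so d = 1.9/2.950 = 0.644, which the SAP gives as 0.64.
- A two-sided t-test at 0.05 with power 0.80 needs 38.84, rounded up to the stated 39 per group.
- The stated 45 is 39 × 1.15 = 44.9, rounded up; 39/0.85 would give 46.

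The PIP sample size therefore reproduces. The documents give no figure for bleeding or for expected exclusions.

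**Assumptions (none from the documents).** Blood loss is lognormal with log-SD 0.6; the RB median is 1.3 times the DB median; DB medians are 200, 300 and 400 mL; 45 patients per arm; all patients above 1000 mL are removed.

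**Step 1: exclusions.** The proportion removed is 1 − Φ((ln 1000 − ln median)/0.6). At a DB median of 400 mL:

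- DB: (6.908 − 5.991)/0.6 = 1.53, giving 6.3%.
- RB (median 520 mL): (6.908 − 6.254)/0.6 = 1.09, giving 13.8%.

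**Step 2: the bleeding contrast.** Without removal, P(RB loss > DB loss) = Φ(ln 1.3/(0.6√2)) = Φ(0.309) = 0.621. After removal, the product of the RB density and the DB distribution function is integrated up to ln 1000 and divided by the two retained proportions.

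**Step 3: the 6-point rating.** Loss was cut at its pooled sextiles (a further assumption), ties counted as one half, and 10,000 trials simulated with a two-sided Mann-Whitney test at 0.05.

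| DB median | Removed, DB v RB | Patients of 45, DB v RB | P(RB > DB), volume | P(RB > DB), 6-point | Power, 6-point |
|---|---|---|---|---|---|
| 200 mL | 0.4% v 1.2% | 0.2 v 0.6 | 0.621 → 0.619 | 0.617 → 0.615 | 0.50 → 0.48 |
| 300 mL | 2.2% v 5.8% | 1.0 v 2.6 | 0.621 → 0.612 | 0.617 → 0.608 | 0.49 → 0.42 |
| 400 mL | 6.3% v 13.8% | 2.9 v 6.2 | 0.621 → 0.604 | 0.617 → 0.600 | 0.50 → 0.35 |

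**Step 4: other inputs.** A second set of eight scenarios used DB medians of 300 or 500 mL, log-SD 0.5 or 0.7, and RB:DB ratios of 1.2 or 1.5. Removal was always more frequent in RB (2% to 34%) than in DB (0.8% to 16%). The log difference among retained patients was 54% to 92% of the true one. Mann-Whitney power on volume (Noether's formula) fell from 0.39 to 0.36 in one of the mildest cases and from 0.74 to 0.38 in the heaviest.

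**Step 5: the primary outcome.** PIP was simulated at the pilot values, with a given within-arm correlation with log loss, and d recomputed after removal.

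| DB median | Correlation 0 | 0.3 | 0.5 |
|---|---|---|---|
| 200 mL | 0.644 | 0.637 | 0.635 |
| 300 mL | 0.644 | 0.629 | 0.619 |
| 400 mL | 0.643 | 0.612 | 0.601 |

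**The case against.** **The wording could mean something else.** The future tense might describe loss anticipated at screening, and the conjunction might require instability and blood loss together. The text also does not say that data are discarded. But a five-minute duration and a loss measured during surgery describe intraoperative events. The joint reading would remove fewer patients than tabulated, without changing the direction. Nothing in the supplied text keeps these patients in the analysis. Part of the SAP was not supplied, so that silence is established only for the text available.

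**The outcome is a rating, not a volume.** This stands as a limit on size. The documents do not link the rating to millilitres. The model makes them agree perfectly: in all three scenarios everyone above 1 L falls in the top category. If surgeons grade the field rather than total loss, the attenuation is smaller.

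**Part of the power loss is only lost numbers.** This is correct. At the 400 mL median, removing equal numbers at random lowers power from 0.50 to 0.45, against 0.35 with selective removal, so about one third of the fall (0.05 of 0.15) is not bias. It is still a consequence of the rule. The drop-out allowance was set for PIP and is 45 − 39 = 6 per arm; in that scenario the expected RB exclusions alone (6.2) would use it up.

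**The stakes are modest.** Bleeding is one of seven secondary outcomes, the bias runs against the sponsor's hypothesis, and nothing in the documents favours the 400 mL scenario for ASA I-II patients with at most three levels. This bears on priority. It does not make the rule sound.

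**Blinding.** Of the anaesthesiologists managing these cases, section 1.5 says "they are not blinded to the group allocation of patients". The documents do not say who applies the exclusion, and its thresholds are numeric, so this is at most a secondary worry.

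**Conclusion.** The concern holds. Applied as written, section 1.3 removes patients after allocation on a variable close to a secondary outcome. If hypotheses (1) and (2) are true, it removes more from RB and biases the bleeding comparison toward no difference. That direction assumes that the removed patients are left out of the analysis and that losses above 1 L go with the worse ratings.

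The size cannot be derived from the documents. Under the assumed loss distributions in the first table, the effect on bleeding is negligible when losses above 1 L are rare and moderate at the 400 mL median; the heavier scenarios of the second set show larger attenuation. For the primary outcome it is small in every scenario of the first set: d stays between 0.60 and 0.64. This should be corrected, but it does not threaten the primary analysis.

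**What to change.** 1. In Protocol section 1.3, keep as exclusion criteria only conditions that can be assessed before allocation.
2. Record blood loss above 1 L and a sustained mean pressure change above 30% as intraoperative events, and report their number by arm.
3. Add to the SAP: all randomised patients are analysed in their allocated group, using all recorded PIP readings, bleeding scores and adverse events.
4. Keep the analysis without these patients as a sensitivity analysis.

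The cost is a change of wording in both documents, with no extra patients or procedures and no change to clinical care. If the current intention is to stop study recording once a threshold is crossed, recording would have to continue in those cases. Data from eventful operations may be somewhat more variable.

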
1.4 Study Flowchart
	<pre> graph TD     A[Patients Enrollment (n=90)] --> B[Group DB (n=45)]     A --> C[Group RB (n=45)]     B --- D["* NMB strategy: - rocuronium 1 mg/kg for induction - maintain deep NMB (TOF count 0, PTC of 1-2)"]     C --- E["* NMB strategy: - rocuronium 1 mg/kg for induction - use of sugammadex to reverse the NMB 10 min after position change (supine → prone) and thereafter, maintain the state of no more use of additional muscle relaxant"]   </pre> 
The flowchart illustrates the study design. It begins with 'Patients Enrollment (n=90)' at the top, which branches into two groups: 'Group DB (n=45)' on the left and 'Group RB (n=45)' on the right. The 'Group DB' box contains the text: '* NMB strategy: - rocuronium 1 mg/kg for induction - maintain deep NMB (TOF count 0, PTC of 1-2)'. The 'Group RB' box contains the text: '* NMB strategy: - rocuronium 1 mg/kg for induction - use of sugammadex to reverse the NMB 10 min after position change (supine → prone) and thereafter, maintain the state of no more use of additional muscle relaxant'.

	
Operation condition assessment
 
1) airway pressure (peak inspiratory pressure)  2) pressure of back muscle retractor  3) the number of body movements  4) the degree of bleeding of each patient scaled by surgeons  5) the muscle tone of each patient scaled by surgeons
 
Reversal of NMB  Sugammadex 4 mg/kg  at the end of the surgery
 
Reversal of NMB  No reversal agent;  but if TOF ratio<0.9  pyridostigmine 10 mg
 
Postoperative assessment
 
 
- recovery time
 
- occurrence of adverse events
 
- overall satisfaction of surgeons
 
	

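### The blinded postoperative assessor is present during emergence, when reversal differs by arm and nothing is masked, so the blinding of recovery time and adverse events is not protected

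*Protocol*

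**What the plan says.** Protocol section 1.5 (Blinding and measure of outcomes) calls the trial double blinded and divides the staff in two. Anesthesia induction and maintenance, including operation of the TOF-Watch, "will be performed by independent anesthesiologists not involved in the study and they are not blinded to the group allocation of patients". After that, "after the end of surgery, a blinded, independent investigator will assess the patients during the emergence and recovery phases". The same paragraph adds: "Postoperative outcomes including recovery time and surgeon satisfaction will be measured by the investigator blinded to the group assignment".

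Reversal is arm-specific:

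- **Group DB:** section 1.5 (NMB) keeps the deep block going "until the end of surgery and the reversal of NMB will be performed by sugammadex 4 mg/kg".
- **Group RB:** sugammadex is given early in the operation, "to reverse the NMB 10 min after position change (10 min after placing the patient prone"). At the end of surgery the section 1.4 flowchart reads "No reversal agent; but if TOF ratio<0.9 pyridostigmine 10 mg".

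On monitoring, section 1.3 says: "The TOF ratio (T4/T1) and T1 value will be displayed on the screen and recorded". Section 1.5 makes a TOF ratio above 0.9 one of the extubation criteria in both arms.

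On timing, section 1.1 defines recovery time as the time to reach sedation score 5 in the PACU, read at 10-minute intervals for an hour. It collects adverse events over the first 24 postoperative hours.

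**The concern.** An assessor's blind is only as good as what the assessor can see. Here the person described as blinded is placed with the patient in the one postoperative phase where the protocol makes the arms look different. A patient given sugammadex at the end of surgery is following the Group DB pathway. A patient given nothing, or pyridostigmine, is following the Group RB pathway.

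What is learned during emergence is carried into the PACU, where the same role scores sedation. A sedation score is a judgement. Section 1.2 also states that the team expects good recovery outcomes in the deep-block group, so an assessor who knew the arm would know the hoped-for direction. Postoperative recovery is in the trial's title. If the blind is not protected, recovery time and adverse-event incidence would be reported as blinded comparisons without a basis for saying so.

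**Working it through.** The plan gives no figure for this point, so the check is to set the sections side by side. The sample size in SAP section 1 has no bearing on it beyond supplying the number of patients.

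**1. Who is present, and when.** Section 1.5 gives the unblinded anesthesiologists induction and maintenance. It names nobody to give the reversal drug or check the extubation criteria. The only person whom the text places in emergence is the blinded investigator.

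**2. What differs by arm in that phase.**

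| Feature | Group DB | Group RB | Source |
|---|---|---|---|
| Block at end of surgery | Deep: TOF count 0 is the target | Reversed earlier; further relaxant only as rescue | 1.5 (NMB) |
| Drug at end of surgery | Sugammadex | None, or pyridostigmine if TOF ratio is below 0.9 | 1.4, 1.5 |
| TOF ratio at extubation | Above 0.9 | Above 0.9 | 1.5 |

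In the flowchart as extracted, the two reversal boxes carry no group label. I assign the second to Group RB by its position, and section 1.5 confirms the first as Group DB. The Group RB sugammadex comes during surgery, before the assessor's stated start, so it does not blur the difference at the end.

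**3. What the assessor could see.** The drug given and the course of the TOF trace differ between arms. The final TOF value does not, since both arms must exceed 0.9.

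**4. What protects the blind.** Neither document describes a masked syringe or dummy injection, a shielded TOF display, a withheld anesthesia record, or a rule that the assessor enters only after reversal.

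**5. Which outcomes are exposed.**

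- *Recovery time:* named in section 1.5 as the blinded investigator's task.
- *Adverse events:* not named there, but section 1.4 lists them with recovery time under postoperative assessment, and section 1.5 gives postoperative outcomes to this investigator.
- *Surgeon satisfaction:* also collected by this investigator, but the rating is the surgeon's own.
- *Peak inspiratory pressure (primary):* measured during surgery, before this assessor's stated start.

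**6. Size.** The phase applies to 45 + 45 = 90 patients. One hour at 10-minute intervals gives 60 / 10 = 6 readings after arrival, so the smallest change a shaded score can make to one patient is 10 minutes. If a fraction f of one arm were scored one step early or late, that arm's mean would move by 10 × f minutes. With f unknown and between 0 and 1, the range is 0 to 10 minutes. The documents give neither f nor a standard deviation for recovery time, so this cannot be turned into an error rate.

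**The case against.** The strongest reply is that nothing in the documents says the assessor gives, watches or is told about the reversal. The flowchart puts Group DB reversal at the end of surgery, while section 1.5 brings the assessor in after the end of surgery, so the reversal may be finished or out of sight. TOF no longer clearly separates the arms once both exceed 0.9. Group RB patients may have had rescue rocuronium or may receive pyridostigmine, so seeing an unlabelled injection would not settle the arm.

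This stands as far as it goes. A reader might infer that the assessments are in fact unblinded, and the documents do not support that. What they show is an unprotected route. The reply does not close it: deep block runs to the end of surgery, so recovery from a TOF count of 0 to a ratio above 0.9 falls in or next to the period when the assessor is present.

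A reader might also infer that attending emergence adds no data and so has no purpose. That goes too far, because an event at emergence can fall within the 24-hour adverse-event window. Moving the assessor to the PACU therefore has a real, small cost.

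Finally, one could keep the assessor in emergence and conceal the drug, the display and the record. That would preserve a single blinded recorder, but it requires several concealment measures to work at the bedside. Later first contact avoids them, and recovery time loses nothing because it is defined in the PACU.

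**Conclusion.** The concern holds as a gap in protection. The protocol claims blinded assessment of recovery time and, by its general wording, of adverse events. Yet it places the assessor in a phase where treatment differs by arm and describes nothing to conceal that difference. The blinding claim for these two secondary outcomes is therefore not secured.

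All 90 patients are potentially affected, with a minimum step of 10 minutes per shaded recovery time. The amount of bias cannot be estimated. The conclusion assumes that no safeguard exists beyond those the two documents describe, and that adverse events fall within the investigator's postoperative outcomes.

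It does not reach the primary endpoint or the surgeons' ratings, and it is not evidence that any assessor learned an allocation. It is worth correcting because the route is avoidable and the correction is cheap.

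**What to change.** Amend the blinding paragraph of Protocol section 1.5 to state that:

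- the blinded investigator first sees the patient on arrival in the PACU, after reversal and extubation;
- the investigator has no access to the anesthesia chart or the TOF-Watch record;
- the investigator rates the sedation score and records adverse events from that point on;
- the unblinded anesthesiologists handle reversal and extubation, and record any adverse event before PACU arrival, flagged as recorded unblinded.

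No reversal drug, dose or extubation criterion changes. The cost is protocol wording, with no additional staff and no loss of any recovery-time reading. The one downside is that adverse events between the end of surgery and PACU arrival are recorded by staff who know the allocation. The flag lets the report show them separately from those recorded blinded.

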## Statistical Analysis Plan

1. Statistical Analysis Plan and Sample Size Justification	
* Statistical Analysis Plan
 
Statistical analyses will be performed using SPSS software (SPSS version 20.0, IBM, Chicago, IL, USA).
 
Student's t-test or Mann-Whitney U-test will be used to compare continuous data including the mean values of the peak inspiratory pressure, the pressure of back muscle retractor and recovery time between the groups. Though measurement timepoints of peak inspiratory pressure and pressure of back muscle retractor are multiple, the mean value of each timepoint will be calculated and the mean value of each group will be analysed by Student's t-test.
 
The normal distribution of the continuous data will be first evaluated using the Shapiro-Wilk test (<math>P > 0.05</math>). The normally distributed data will be analysed using the Student's t-test, and the abnormally distributed data will be analysed using the Mann-Whitney U-test.
 
Ordinal variables including, the degree of bleeding of each patient scaled by surgeons, assessed using a 6-point scale and overall satisfaction of surgeons, assessed using numerical rating scale (NRS; 1-10) will be compared using the Mann-Whitney U-test. Categorical variables such as the muscle tone of each patient scaled by surgeons, assessed using a 3-point scale, the number of body movements during the surgery and the incidence of adverse events between the groups will be compared using a chi-squared test (or Fisher's exact test).
 
The data will be expressed as the mean <math>\pm</math> standard deviation, median (25; 75 quartiles), or number of patients (%). P-values will be reported as two-tailed values and a P-value <math>< 0.05</math> will be considered statistically significant.
 
* Sample size calculation
 
Primary endpoint in this study is mean value of peak inspiratory pressure during the surgery. The sample size calculation was based on the results of a pilot study with 10 cases in each group. In the pilot study, peak inspiratory pressure (mean <math>\pm</math> standard deviation) was <math>18.8 \pm 2.9</math> cmH2O in Group DB and <math>20.7 \pm 3.0</math> cmH2O in Group RB, respectively. Therefore, the effect size of 2-groups was 0.64. On the assumption that the allocation ratio of 2-groups was 1, a sample size of 39 patients was selected for each group, calculated by Student's t-test, two-sided test, a level of significance of 0.05 and a power of 0.8. We estimated a 15% drop-out, resulting in the final enrolment of 45 patients in each group (total, 90 patients).

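### Rescue rocuronium is recorded but named in no planned comparison, so the tone and movement comparisons may understate failures of restricted block

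*Protocol*

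**What the plan says.** Protocol 1.5 states the rescue rule twice, under blinding and measurement of outcomes and again under NMB for Group RB. In both places the trigger is any body movement or a surgeon's complaint of grade-3 tone, and the consequence is the same: "rescue rocuronium 5 mg will be administered and the number of body movements and rescue rocuronium administration (dose) will be recorded". The first statement names no group. The second is an exception to the ban on further relaxant in Group RB. The flowchart in Protocol 1.4 shows Group RB with no further relaxant after reversal and shows no exception.

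Rescue is not among the eight outcomes in Protocol 1.1. Movement is an outcome over the whole operation: "The Number of Body Movements [Time Frame: Throughout the surgery". Muscle tone is an outcome only at pedicle screw insertion. PIP and retractor pressure are read every 15 minutes, with no cut at rescue.

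The SAP tests tone and movement as categorical variables. For movement, "the number of body movements during the surgery and the incidence of adverse events between the groups will be compared using a chi-squared test", or by Fisher's exact test. The SAP text names neither a comparison of rescue nor a rule for data after rescue. Part of the SAP file was not available to me, so this silence is judged on its section 1.

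**The concern.** Hypothesis (2) is that operating conditions, including movement and tone, are better under deep block. The clearest evidence that restricted block has failed is that relaxant had to be given again. That event is written down but is not used in any named analysis.

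The two outcomes that stand in for it are themselves altered by it. Rescue for a tone complaint during exposure can improve the tone scored later at screw insertion, and it can prevent a movement that would otherwise have occurred. A Group RB patient may then enter both tests as a success although the strategy had to be supplemented. If this happens mainly in Group RB, both comparisons move towards no difference. A reader of the results could not tell how often it happened.

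**Working it through.** **1. What each planned analysis sees.** Possible courses of a Group RB patient, from the time frames in Protocol 1.1 and the rescue rule in 1.5:

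| Course | Any movement | Tone at screw insertion | Any rescue |
|---|---|---|---|
| Moves, then rescued | Yes | May be improved by rescue | Yes |
| Grade-3 complaint before screw insertion, rescued, later moves | Yes | May be improved by rescue | Yes |
| Grade-3 complaint first arises at screw insertion, never moves | No | Grade 3 | Yes |
| Grade-3 complaint before screw insertion, rescued, never moves, tone then acceptable | No | Acceptable | Yes |
| No complaint, no movement | No | Acceptable | No |

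The fourth row is the gap: only the rescue record separates that patient from the fifth row. If movement is analysed as yes or no, a first movement cannot be suppressed by the rescue it triggers, so only an earlier tone-triggered rescue can change that patient's status. If movement is analysed as a count, any rescue can also suppress later movements.

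**2. Size of the gap.** Let t be the share of Group RB following the fourth row. The documents do not give it. With 39 evaluable patients, the failures missed are 39 × t:
- t = 5%: 39 × 0.05 = 2.0 patients
- t = 10%: 39 × 0.10 = 3.9 patients
- t = 20%: 39 × 0.20 = 7.8 patients

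**3. The plan's sample size.** Inputs from the SAP: "The sample size calculation was based on the results of a pilot study with 10 cases in each group", with PIP 18.8 (SD 2.9) in DB and 20.7 (SD 3.0) in RB; "two-sided test, a level of significance of 0.05 and a power of 0.8"; "the allocation ratio of 2-groups was 1".
- Effect size: 1.9 / √((2.9² + 3.0²)/2) = 1.9 / 2.95 = 0.644. The SAP says "the effect size of 2-groups was 0.64".
- n per arm by the normal formula: 2 × (1.960 + 0.842)² / 0.64² = 38.3, rounded up to 39. The SAP says "a sample size of 39 patients was selected for each group". The noncentral t gives 39.3, so 40.
- Drop-out: 39 × 1.15 = 44.85, so 45 as stated. (39 / 0.85 = 45.9 would give 46, which does not matter here.)

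The plan's figures reproduce. Noncentral-t power at 0.64 is 79.7% with 39 per arm and 85.1% with 45.

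**4. What rescue could do to PIP power.** Let L be the share of the contrast lost: the proportion of RB rescued, times the share of their readings after rescue, times the share of the effect that rescue removes. The effect size becomes 0.64 × (1 − L). All three factors are assumptions.

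| L | Effect size | Power, 39 per arm | Power, 45 per arm |
|---|---|---|---|
| 0 | 0.640 | 79.7% | 85.1% |
| 5% | 0.608 | 75.5% | 81.4% |
| 10% | 0.576 | 70.9% | 77.1% |
| 15% | 0.544 | 66.0% | 72.3% |
| 30% | 0.448 | 49.7% | 55.6% |

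Nothing in the documents places L in this table. If the pilot used the same rescue rule, 0.64 already includes the effect and the first row applies.

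**5. Could a rescue comparison show anything?** Fisher's exact test, 39 per arm, assuming no rescue in DB: power is 19% if 10% of RB are rescued, 54% at 15%, 82% at 20% and 99% at 30%.

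**The case against.** The strongest reply is that both rescue triggers are already secondary outcomes and both are tested. Every movement-triggered rescue leaves a counted movement. Because the SAP treats movement as categorical, the natural reading is patients with and without movement, and treating a first movement cannot alter that. This stands. A reader might infer that the failures of restricted block are hidden, but the documents do not support that. What can go unseen is narrower: tone complaints away from screw insertion, movements prevented by rescue, and the frequency and dose of rescue.

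The second reply is that Protocol 1.5 writes rescue into the Group RB strategy, so comparing the groups as managed, with every reading kept, answers a legitimate question. This also stands. A reader might infer that the primary PIP contrast is diluted and the trial underpowered. Dilution exists only against a no-rescue comparison that the protocol never states. The depth of block after 5 mg is not given; at assumed weights of 50 to 80 kg, 5 mg is 5/50 = 10% down to 5/80 = 6% of the induction dose. Any attenuation would also work against the deep-block hypothesis, so it would not create a false positive.

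The third reply is that the SAP's lists of variables are open-ended, so a rescue comparison is not excluded. That is true, but a comparison not named in advance is one the analyst may make or leave out after seeing the data. None of the three replies covers the patient rescued for tone before screw insertion who never moves.

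**Conclusion.** The point holds for the tone and movement comparisons. As written, the plan can count a tone-triggered rescue as no failure in either, so these tests of hypothesis (2) may understate how often restricted block fails. The expected direction is towards no difference. That assumes rescue works at least in part and is commoner in RB than in DB.

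The size cannot be fixed from the documents. It is 39 × t patients, about 2 to 8 for an assumed t of 5% to 20%, and it could be close to zero.

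The point does not extend to the primary analysis. The all-readings PIP and retractor comparisons are valid for the strategies as managed, and the power losses in the table above are conditional on assumptions, not findings. The plan should nevertheless say that this is the question being asked, because the flowchart describes Group RB without the rescue exception.

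**What to change.** 1. Add to the SAP a secondary comparison by arm of patients needing at least one rescue dose for movement or grade-3 tone (chi-squared or Fisher's exact test), and report total rescue dose by arm.
2. Add a yes/no composite by arm: any movement or any rescue. Occurrence and dose are already recorded, and the reason is not needed for either item.
3. Keep all readings in the main PIP and retractor analyses, and state that rescue is counted as part of the strategy. A PIP analysis restricted to readings before rescue is optional and only supportive: it selects on a post-randomisation event, and it needs rescue times that the protocol does not say are collected.
4. Reconcile Protocol 1.4 and the two statements in 1.5 on whether relaxant may be given after reversal and on which group the rescue rule covers. Do this before finalising items 1 and 2. If the rule covers Group RB alone, rescue in DB is zero by definition and the comparison is not like for like; grade-3 complaints would then have to be recorded in both arms to make it so. If it covers both, rescue doses in DB must be distinguishable from maintenance doses.

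The cost is SAP wording, one clarification of the protocol, and one or two more secondary comparisons, which add to multiplicity. The sample size and primary analysis do not change. This review proposes no change to the rescue rule itself.
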